1.3 Schedule of activities (SoA)

The Assessment Schedule (Table 1-2) lists all of the assessments when they are performed. All data obtained from these assessments must be supported in the participant's source documentation. The "X" in the table denotes the assessments to be recorded in the clinical

database or received electronically from a vendor. The "S" in the table denotes the assessments that are only in the participant's source documentation and do not need to be recorded in the clinical database.

Sacubitril/valsartan treatment will start at Visit Day1, which is the same day as the End of Study visit (Visit 599) of CLCZ696B2319E1 (PANORAMA-HF OLE) study. A telephone visit (Visit M3) and an on-site visit (Visit M6) will occur 3 months and 6 months after Visit Day1, respectively. The visits as same Visit M3 and Visit M6 will then be repeated every 3 months until the end of the study. When the pediatric formulation of sacubitril/valsartan becomes available in Japan, or this study is terminated by Novartis, any participants should return to the study site as soon as possible for End of Study (EOS) visit (Visit EOS) regardless of subsequent scheduled visit, and all of the assessments listed for Visit EOS will be performed.

Participants should take their scheduled dose of sacubitril/valsartan in the morning of their study visits. Participants are not required to fast overnight on the day prior to or the day of the study visit.

Participants should be seen for all visits/assessments as outlined in the assessment schedule or as close to the designated day/time as possible. If one visit is postponed or brought forward, it should not result in the next visit being postponed or brought forward. The next visit, if at all possible, should adhere to the original schedule in relation to Visit Day1. Missed or rescheduled visits should not lead to automatic discontinuation. Specific circumstances surrounding missed or rescheduled visits must be discussed with the study monitor. Participants who prematurely discontinue the study treatment, or prematurely withdraws from the study for any reason should be scheduled for a final visit as soon as possible, at which time all of the assessments listed for the final visit (Visit EOS) will be performed.

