As per Section 4.5, during a public health emergency as declared by local or regional authorities i.e. pandemic, epidemic or natural disaster that limits or prevents on-site study visits, alternative methods of providing continuing care may be implemented by the Investigator as the situation dictates. If allowable by a local health authority, national and local regulations and depending on operational capabilities, phone calls, virtual contacts (e.g. tele consultation) or visits by site staff/ off-site healthcare professional(s) staff to the participant's home, can replace on-site study visits, for the duration of the disruption until it is safe for the participant to visit the site again. If the Investigator delegates tasks to an off-site healthcare professional, the Investigator must ensure the individual(s) is/are qualified and appropriately trained to perform assigned duties. The Investigator must oversee their conduct and remain responsible for the evaluation of the data collected.

Table 1-2 Assessment Schedule

Period			Treatment		
Visit name	Day1#.1	M3 †	M6*	UNS	EOS2
Day/ Month	Day 1	Mo 3	Mo 6	-	-
Obtain Informed Consent (parent (s)- legal guardian (s)/consent-assent (patient, as applicable) ³	х				
Inclusion/ Exclusion	Х				
Demographics/ Medical histories	Х				
Pediatric Heart Failure History	Х				
Physical Examination	s		s	s	S
Vital Signs (BP and pulse)	X 5		Х	Х	Х
Height ⁴	X 5		S	(S)	Х
Weight	X 5		Х	Х	Х
Laboratory assessments (locally) ⁶			Х	(X)	Х
Serum/Urine Pregnancy test (locally) 7			S (Urine)	S (Urine)	S (Serum)
AEs/SAEs	Х	Х	Х	Х	Х
Concomitant medication/ Non-drug therapies	х	х	х	х	х
Dosage Administration Record	Х	Х	Х	(X)	Х
Study Medication Compliance	S		S	(S)	S
Dispense Study Medications	s	S	S	(S)	

UNS= Unscheduled visit, EOS= End of study visit

- X: Assessment to be recorded in the clinical database or received electronically from a vendor
- S: Assessment to be recorded in the source documentation only
- (X) / (S) = parentheses indicate that this is an optional assessment
- # Visit Day1 is the same day as Visit 599 (EOS visit) of PANORAMA-HF OLE (CLCZ696B2319E1) study
- † Visit M3 is a telephone visit.
- * If the trial is extended, Visits M9, M12 to be performed at the same intervals and with same measurements as at Visits M3 and M6, respectively.

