7. For child-bearing potential females (CHBP) only. Urine pregnancy test is analyzed locally and done at Visit M6 and unscheduled visits on all female participants ≥11 years of age and all female participants who are <11 years of age if they are menstruating. There is no assessment at Visit Day1, but the result of central laboratory (serum test) at the End of Study visit (Visit 599) in PANORAMA-HF OLE study should be reviewed by the Investigator soon after the result is obtained. Additionally, for all CHBP, a urine pregnancy test will be performed at monthly intervals during the study. The monthly urine pregnancy test can be performed either via: 1) monthly study site visits for urine pregnancy tests, or 2) providing the participant with urinary pregnancy tests for home monthly tests. See Section 8.4.5 for additional details. A serum pregnancy test is performed and analyzed locally at Visit EOS.

2 Introduction

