Females are considered post-menopausal if they have had 12 months of natural (spontaneous) amenorrhea with an appropriate clinical profile (e.g. age-appropriate history of vasomotor symptoms). Females are considered not of child-bearing potential if they are post-menopausal or have had surgical bilateral oophorectomy (with or without hysterectomy), total hysterectomy or bilateral tubal ligation at least six weeks prior to enrollment on study. In the case of oophorectomy alone, only when the reproductive status of the female has been confirmed by follow-up hormone level assessment is she considered to be not of child-bearing potential.

If local regulations are more stringent than the contraception methods listed above to prevent pregnancy, local regulations apply and will be described in the informed consent form (ICF).

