8.4.5 Pregnancy testing

All child-bearing potential female participants who are not surgically sterile will have pregnancy testing. Additional pregnancy testing might be performed if requested by local requirements.

Childbearing potential females (CHBP) are defined as all female participants ≥ 11 years of age and all female participants who are <11 years of age if they are menstruating. Pre-menarchal girls <11 years of age should notify the study site if they start menstruating after the study has started so pregnancy testing can be initiated. Urine pregnancy test is analyzed locally and done at all in-person scheduled/unscheduled visits (except for End of Study visit: Visit EOS) on all CHBP female participants. There is no assessment at Day1, but the result of central laboratory (serum test) at the End of Study visit (Visit 599) in PANORAMA-HF OLE study should be reviewed by the Investigator soon after the result is obtained. A positive urine pregnancy test should be confirmed with a serum pregnancy test. Participants with a positive serum pregnancy at any time in the study must be discontinued immediately from the study and should be seen at the site for Visit EOS. Serum pregnancy testing will be performed at Visit EOS.

For child-bearing potential females, a urine pregnancy test will also be performed at monthly intervals between study visits, during the study. The between-study-visit monthly urine pregnancy test can be performed either via: 1) monthly study site visits for urine pregnancy tests, or 2) providing the participant with urinary pregnancy tests for home monthly tests.

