Medical documentation of oophorectomy, hysterectomy, or tubal ligation must be retained as source documents. Subsequent hormone level assessment to confirm the female is not of child-bearing potential must also be available as source documentation in the following cases:

- 1. Surgical bilateral oophorectomy without a hysterectomy
- 2. Reported 12 months of natural (spontaneous) amenorrhea with an appropriate clinical profile.

In the absence of the above medical documentation, Follicle Stimulating Hormone (FSH) testing is required of any female participant regardless of reported reproductive/menopausal status at screening/baseline.

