9.2.2 Participant demographics and other baseline characteristics

Demographic and other characteristics at Visit Day1, including age, age group (6 years and older, < 6 years), sex, weight, height, body mass index (BMI), vital signs, and age adjusted percentile for weight and height, and z-score for height will be summarized descriptively.

BMI will be calculated as weight (kg) / height² (m²) using the collected height and weight at Visit Day1.

Relevant medical histories at Visit Day1 will be summarized, by system organ class and preferred term.

The SAF will be used for the above analyses.

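### As worded, the last sentence of Protocol 8.4.5 requires FSH testing of every girl without sterilisation or hormone-confirmed amenorrhoea records, pre-menarchal girls under 11 included, and for most of them no rule uses the result

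*Protocol*

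**What the plan says.** Protocol 8.4.5 sets pregnancy testing by age and menstruation: "Childbearing potential females (CHBP) are defined as all female participants ≥ 11 years of age", together with younger girls who already menstruate. For the rest, "Pre-menarchal girls <11 years of age should notify the study site if they start menstruating after the study has started", and testing begins then.

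The section closes with a paragraph on source documents. Records of oophorectomy, hysterectomy or tubal ligation must be kept. A hormone result must also be available in two cases: bilateral oophorectomy without hysterectomy, and reported 12-month natural amenorrhoea. The last sentence then states that, without this documentation, "Follicle Stimulating Hormone (FSH) testing is required of any female participant regardless of reported reproductive/menopausal status at screening/baseline".

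Elsewhere, Protocol 5.2 uses a hormone level only after oophorectomy alone, where a female counts as not of child-bearing potential "only when the reproductive status of the female has been confirmed by follow-up hormone level assessment". Protocol 1.3 says that "The Assessment Schedule (Table 1-2) lists all of the assessments when they are performed". Table 1-2 does not mention FSH, although its footnote 7 on pregnancy testing adds "See Section 8.4.5 for additional details". Protocol 8.5 states that there are no additional tests. The SAP does not mention FSH.

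**The concern.** The population is under 18 at consent. A typical girl has no sterilisation record and no hormone-confirmed amenorrhoea, so the condition that triggers the FSH sentence is met by default. The sentence then applies to *any* female, *regardless of* what she reports. One section thus excuses a pre-menarchal girl under 11 from a urine pregnancy test and, a few paragraphs later, requires a hormone test of her.

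What is at stake is practical. A site that obeys the words tests a child with heart failure for a result that decides nothing. A site that follows the probable intent departs from an instruction worded as a requirement. Sites may also act differently from one another.

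**Working it through.** The plan gives no figure to reproduce. The check is a comparison of texts, with a simple bound on size.

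1. **Who is caught by the words.** The trigger is absence of the listed documents (8.4.5, last paragraph). The scope is any female participant. No age, menarche or claimed-status limit is stated. A girl with none of the listed records is therefore covered, whatever her age.

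2. **Whether such girls are foreseen.** They are. 8.4.5 gives instructions for pre-menarchal girls under 11. Protocol 9.2.2 also tabulates two age groups, under 6 and 6 or older. That is a reporting category and does not show that any girl under 6 will enrol.

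3. **What the result would be used for.**
   - Child-bearing potential for pregnancy testing (8.4.5): set by age and menstruation; FSH is not used.
   - Eligibility (5.2): a hormone level is used only after oophorectomy alone.
   - Source documents (8.4.5): a hormone level is needed after oophorectomy without hysterectomy or for 12-month amenorrhoea.
   - FSH cut-off: none given.
   - SAP: no FSH analysis or listing.

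   For a girl who claims neither sterilisation nor amenorrhoea, no eligibility, contraception, pregnancy-testing or analysis rule takes the value as input.

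4. **Where it is scheduled.** Table 1-2 has 15 assessment rows and 7 numbered footnotes. FSH is in 0 of 15 and 0 of 7. In the protocol FSH is named in 2 places: 8.4.5 and the abbreviation list (10.2.1). Footnote 6 names sodium, potassium, creatinine and eGFR as the required laboratory tests. Footnotes 6 and 7 say that no local laboratory or pregnancy assessment is done at Visit Day1.

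5. **Size.** Let g be the number of girls without the listed records. The enrolment cap is 8 (Protocol 9.9.1), so 0 ≤ g ≤ 8; g is not given. Tests required by the words = g. Tests shown in Table 1-2 = 0. The mismatch is g − 0 = g, at most 8 and possibly 0.

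6. **After the change proposed below.** Let c be the number of females who claim status by oophorectomy without hysterectomy or by 12-month amenorrhoea and have no hormone result on file. Tests required = c. These females also fall under the present sentence, so c ≤ g, and the tests spared number g − c.

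**The case against.** The strongest reply is that the sentence should be read in its paragraph. That paragraph concerns proof that a female is *not* of child-bearing potential, and the sentence opens by referring back to that proof. On this view it is a fallback for undocumented claims, and the phrase on reported status means only that a verbal report does not replace a record. 8.4.5 has already classified girls by age and menstruation. This is a plausible account of the intent, and I accept it as the likely one. It does not settle the matter, because *any* and *regardless of* state a wider rule, and sites and monitors work from the words.

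Three further points for the plan stand, and each limits what can be claimed.

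- **Timing.** A reader might infer a mandated baseline blood test. The words on screening or baseline directly follow the reported status and may describe when that status was reported. If so, the test has no stated time. Nor is a separate venepuncture shown to be needed, since Visit Day1 falls on the same day as Visit 599 of the preceding study.
- **Table 1-2.** A reader might take the missing entry as an error in its own right. A conditional test need not have its own row: the serum test that confirms a positive urine test has none either. Footnote 7 sends sites to 8.4.5, so the rule can be found. The omission matters only because the words make the test near-universal.
- **Deviations.** A reader might infer that each omitted test is a countable protocol deviation. SAP 2.3.1 does count patients with deviations, but no text makes a missing FSH test one. SAP Table 5-1 lists four deviations that lead to exclusion from an analysis set, three on consent and one on age, so no analysis set would change.

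**Conclusion.** The point holds as a minor matter of wording. The last sentence of 8.4.5 requires more than the rest of the protocol can use, and it sits badly with that section's own classification by age and menstruation and with 8.5. The consequence is an unneeded test, or a departure from a stated requirement, in at most 8 participants.

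This rests on two assumptions: that at least one girl without the listed records enrols, which the documents neither show nor rule out, and that a site reads the sentence as written. The adverse event endpoint and its summaries are unaffected. A reader might go further and see a threat to the safety results or to the analysis sets; nothing in the protocol or SAP supports that.

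**What to change.** Replace the last sentence of 8.4.5 with:

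> FSH testing is required only for a female who claims non-child-bearing status on the basis of bilateral oophorectomy without hysterectomy or 12 months of natural amenorrhea and has no hormone result on file. Females with documented surgical sterilisation are handled as in Section 5.2. All remaining female participants are classified by age and menstruation as above and need no FSH test.

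Add to Table 1-2 footnote 7:

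> FSH only if required by Section 8.4.5.

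The middle sentence of the replacement is needed. Without it, a girl aged 11 or over with documented sterilisation would be classed as of child-bearing potential, against Section 5.2. Exclusion criterion 8 and the opening of 8.4.5, which exempts surgically sterile females from pregnancy testing, stay as they are.

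The cost is one short passage and one footnote clause, with no new visit or assessment. There is one small downside. A female who reports hysterectomy or tubal ligation without records loses the FSH fallback; she is instead classified, and pregnancy-tested, by age and menstruation.

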8.4.6 Other safety evaluations

Not applicable

8.4.7 Appropriateness of safety measurements

The safety and clinical laboratory assessments performed in this study are similar to those used in PANORAMA-HF OLE study. These assessments are appropriate for an investigational drug with the mechanism(s) of action of sacubitril/valsartan (angiotensin receptor neprilysin inhibitor), the safety profile described in LCZ696 Investigator's Brochure (IB), and the indication/participant population under study.

8.5 Additional assessments

No additional tests will be performed on participants entered into this study.

8.6 Adverse events (AEs), serious adverse events (SAEs), and other safety reporting

The definitions of AEs and SAEs can be found in Section 8.6.

AEs will be reported by the participant (or, when appropriate, by a caregiver, surrogate, or the participant's legally authorized representative).

The Investigator and any qualified designees are responsible for detecting, documenting, and recording events that meet the definition of an AE or SAE and remain responsible for following up (see Section 7).

The method of recording, evaluating, and assessing causality of AEs and SAEs and the procedures for completing and transmitting SAE reports are provided in Section 8.6.3.

8.6.1 Adverse events

An AE is any untoward medical occurrence (e.g. any unfavorable and unintended sign [including abnormal laboratory findings], symptom or disease) in a clinical investigation participant after providing written informed consent for participation in the study. Therefore, an AE may or may not be temporally or causally associated with the use of a medicinal (investigational) product.

The Investigator has the responsibility for managing the safety of individual participant and identifying adverse events.

Novartis qualified medical personnel will be readily available to advise on trial-related medical questions or problems.

The occurrence of adverse events must be sought by non-directive questioning of the participant at each visit during the study. Adverse events also may be detected when they are volunteered by the participant during or between visits or through physical examination findings, laboratory test findings, or other assessments.

Adverse events must be recorded under the signs, symptoms, or diagnosis associated with them, accompanied by the following information (as far as possible) (if the event is serious refer to Section 8.6.2):

- 1. The severity grade
- mild: usually transient in nature and generally not interfering with normal activities
- moderate: sufficiently discomforting to interfere with normal activities
- severe: prevents normal activities
- 2. Its relationship to the study treatment and other investigational treatment. If the event is due to lack of efficacy or progression of underlying illness (i.e. progression of the study indication) the assessment of causality will usually be 'Not suspected.' The rationale for this guidance is that the symptoms of a lack of efficacy or progression of underlying illness are not caused by the trial drug, they happen in spite of its administration and/or both lack of efficacy and progression of underlying disease can only be evaluated meaningfully by an analysis of cohorts, not on a single participant
- 3. Its duration (start and end dates or ongoing) and the outcome must be reported
- 4. Whether it constitutes a SAE (see Section 8.6.2 for definition of SAE) and which seriousness criteria have been met
- 5. Action taken regarding with study treatment.

All adverse events must be treated appropriately. Treatment may include one or more of the following:

- Dose not changed
- Dose Reduced/increased
- Drug interrupted/permanently discontinued
- 6 Its outcome

Conditions that were already present at the time of informed consent should be recorded in medical history of the participant.

Adverse events (including lab abnormalities that constitute AEs) should be described using a diagnosis whenever possible, rather than individual underlying signs and symptoms.

Adverse event monitoring should be continued for at least 30 days following the last dose of study treatment.

Once an adverse event is detected, it must be followed until its resolution or until it is judged to be not recovered/not resolved (e.g. continuing at the end of the study), and assessment must be

made at each visit (or more frequently, if necessary) of any changes in severity, the suspected relationship to the interventions required to treat it, and the outcome.

Information about adverse drug reactions for the investigational drug can be found in the IB.

Abnormal laboratory values or test results constitute adverse events only if they fulfill at least one of the following criteria:

- they induce clinical signs or symptoms
- they are considered clinically significant
- they require therapy

Clinically significant abnormal laboratory values or test results must be identified through a review of values outside of normal ranges/clinically notable ranges, significant changes from baseline or the previous visit, or values which are considered to be non-typical in participant with the underlying disease. Alert ranges for laboratory and other test abnormalities are included in Section 10.3.

8.6.2 Serious adverse events

An SAE is defined as any adverse event [appearance of (or worsening of any pre-existing)] undesirable sign(s), symptom(s), or medical conditions(s) which meets any one of the following criteria:

- fatal
- life-threatening

Life-threatening in the context of a SAE refers to a reaction in which the participant was at risk of death at the time of the reaction; it does not refer to a reaction that hypothetically might have caused death if it were more severe (please refer to the ICH-E2D Guidelines).

- results in persistent or significant disability/incapacity
- constitutes a congenital anomaly/birth defect, fetal death or a congenital abnormality or birth defect
- requires inpatient hospitalization or prolongation of existing hospitalization, unless hospitalization is for:
 - routine treatment or monitoring of the studied indication, not associated with any deterioration in condition
 - elective or pre-planned treatment for a pre-existing condition that is unrelated to the indication under study and has not worsened since signing the informed consent
 - social reasons and respite care in the absence of any deterioration in the participant's general condition
 - treatment on an emergency outpatient basis for an event not fulfilling any of the definitions of a SAE given above and not resulting in hospital admission
- is medically significant, e.g. defined as an event that jeopardizes the participant or may require medical or surgical intervention to prevent one of the outcomes listed above

Medical and scientific judgment should be exercised in deciding whether other situations should be considered serious reactions, such as important medical events that might not be immediately

life-threatening or result in death or hospitalization but might jeopardize the participant or might require intervention to prevent one of the other outcomes listed above. Such events should be considered as "medically significant." Examples of such events are intensive treatment in an emergency room or at home for allergic bronchospasm, blood dyscrasias, or convulsions that do not result in hospitalization or development of dependency or abuse (please refer to the ICH-E2D Guidelines).

All new malignant neoplasms will be assessed as serious under "medically significant" if other seriousness criteria are not met and the malignant neoplasm is not a disease progression of the study indication.

All reports of intentional misuse and abuse of the product are also considered serious adverse events irrespective of whether a clinical event has occurred.

Any suspected transmission via a medicinal product of an infectious agent is also considered a serious adverse reaction.

